The proposal is for a real life clinical practice study in which female participants with a predefined history of recurrent UTIs in the previous year will be treated with 3 months of oral vaccine with a further 9 months of follow-up. The primary outcome will be no UTI in the 12 months following initiation of the vaccine (definition of a responder). A clinically significant and important outcome will be defined as a responder rate of 50% (50% of participants who had at least 3 UTIs in the previous year reporting no UTIs after therapy initiated.

Study Protocol

Study Participants

Main Inclusion Criteria:

Eligible participants will include women with at least 3 reported UTI episodes requiring antibiotics in the preceding 12 months or at least 2 reported UTI episodes requiring antibiotics in the preceding 6 months. In both cases, at least one of the episodes must be associated with a positive urine culture with a traditional and accepted uropathogen.

Other inclusion Criteria:

- Female participant \geq 18 and \leq 75 years of age at time of screening.
- Can provide written consent and willingness to comply with all aspects of study treatment and study requirements.
- Individuals who have had at least 3 episodes of a UTI in the past 12 months or 2 UTI episodes in the past 6 months. At least one of the UTI episodes must be associated with a positive urine culture with a traditional uropathogen including Escherichia coli, Proteus spp., Staphyloccous sp., Enterococcus sp., Klebsiella sp., or Pseudomonas aeruginosa.
- Post-menopausal for a minimum of 1 year or negative pregnancy test if participant is of child bearing potential and agreement to acceptable contraceptive use from Screening Visit 1 to final follow up visit if

participant is sexually active. Medically acceptable methods of contraception include hormonal contraception (i.e. estrogen, and/or progesterone or preparations that contain a combination of these hormones), non-hormonal intrauterine device or double barrier method (i.e. condom with foam or vaginal spermicidal suppository, or diaphragm with spermicide) or vasectomy of sole sexual partner. Complete abstinence alone can be used as a method of contraception.

• Free of a urinary tract infection at the time of trial inclusion.

Exclusion Criteria

- History of bladder tumours including uterine, cervical, vaginal or urethral cancer.
- Worrisome post-voiding residual (investigator's discretion).
- Infection related to urinary lithiasis.

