Temperature excursions outside of the accepted range will be immediately reported to the Investigator, [name] and the study drug affected will be quarantined. Documentation of the excursion is to be recorded and sent to [name] by email or in person for review and determination of continued use of the study drug. [name] will consult with Red Leaf Medical.

Dosage and Administration (Day 1)

Once all Baseline Visit procedures are completed eligible participants will receive a 3 month supply of Uromune® treatment. Participants will be instructed to take 2 sprays of the treatment under their tongue, once daily for 3 months (90 days). The liquid is to be held under the tongue for 2 minutes without swallowing. After the 2 minutes has passed the liquid is to be swallowed. The Uromune® treatment is to be taken before breakfast each day to avoid mixing it with foods or beverages.

If a dose is missed, participants should take the dose as soon as they remember on the same day and inform the study staff. However, if it is the next day, the missed dose should be skipped and the next dose taken as normal. **Only one dose of study drug (2 sprays) should be taken each day** and a double dose should not be taken.

Study Treatment Compliance

Participant compliance with the study treatment will be assessed through a review of the participant's Treatment Diary during their 3 month clinic visit. At the 3 month clinic visit, the participant will return the study treatment bottle and any unused study treatment.

Drug Accountability

The investigator will be responsible for product accountability. Site staff will be required to maintain a drug accountability log throughout the duration of the study. These records shall include dates, quantities, batch numbers, and expiry dates, receipt date of study medication at site, dispense date of study drug to each participant and return date of each participants study drug.

Safety Reporting

The investigator is responsible for the detection and documentation of events meeting the criteria and definition of an AE or SAE. The research coordinator will record all clinical AEs, noted during the trial, on the AE event log, report to the Investigator, [name], and enter into the electronic data capture database (EDC). All adverse events will be reported to the ethics board as per local guidelines.

For this study, the following standard AE definitions are used:

Adverse Event (AE)

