An AE, also known as an adverse experience, is defined as any untoward medical occurrence in a patient or clinical investigation participant administered a pharmaceutical product and which does not necessarily have to have a causal relationship with this treatment (ICH GCP/Health Canada Division 5).

An AE can therefore be any unfavorable and unintended sign, symptom, abnormal results of an investigation, or disease (new or exacerbated) temporally associated with the use of the investigative product, without any judgement on causality

Events that do not meet the definition of an AE include:

- Medical or surgical procedures; the condition that leads to the procedure is an AE.
- Anticipated day-to-day fluctuations of a pre-existing disease or condition present at the start of the study that do not worsen.
- The disease/disorder being studied (eg. Recurrent urinary tract infections) or expected progression, signs or symptoms of the disease being studied, unless more severe than expected for the participant's condition.

AEs that are serious, unexpected and at least possibly related to study participation will be reported to the Research Ethics Board and to Health Canada within the timelines indicated below.

All other AEs such as those that are not serious, expected and not related to the study participation will not be reported to the local Research Ethics Board, as per local guidelines.

Serious Adverse Event Definition/ Reporting Requirements

An adverse event is considered serious if any untoward medical occurrence includes any of the following:

- a) Results in death: This includes any death that occurs while the participant is in the study.
- b) Is immediately life-threatening.
 When in the view of the Investigator, the AE places the participant at immediate risk of death. It does not include a reaction that had it occurred in a more severe form, might have caused death.
- c) Event requires in-patient hospitalization or prolongation of existing hospitalization.

In the absence of an AE, hospitalization or prolongation of hospitalization should not be reported as an SAE in the following circumstances:

- Hospitalization or prolongation of hospitalization is part of a routine procedure followed by the study centre.
- Hospitalization for survey visits or annual physicals.
- For hospitalization planned and documented before the start of the study for preexisting condition which has not worsened.
- d) Is a congenital anomaly/birth defect.

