- e) Results in persistent or significant disability or incapacity.
- f) Is an important medical event that may jeopardize the patient or may require medical intervention to prevent one of the outcomes listed above.

Recording Adverse Events

All adverse events, which include any detrimental change in the participant's condition, will be collected from the time the participant signs the consent form until the follow up period is completed at the 12 month clinic visit.

AEs will be captured wherever possible as a diagnosis and it is the Investigator's responsibility to ensure this is done. All AEs including SAEs are to be accurately recorded on the Adverse Event case report form(s). The Investigator will carefully evaluate each AE to determine severity, expectedness, relatedness and outcome as indicated below.

Severity:

- Grade 1 Mild: Participant is aware symptoms but they are easily tolerated and have no or mild impact on regular activities. Symptoms do not require medical attention or treatment.
- Grade 2 Moderate: An event the participant experiences that is of minor concern or convenience. These events may have an impact on Page 12 of 24

daily activities but can typically be improved with simple therapeutic measures. These experiences may interfere with the participant's normal functioning.

- Grade 3 Severe: These events are usually incapacitating to the participant. They impact normal daily activities and typically require treatment or systemic drug therapies.
- Grade 4: Life threatening or disabling.
- Grade 5: Death

Expectedness

AEs must be classified based on whether or not they were expected given current knowledge of the study treatment and procedures:

- Unexpected: The event is not expected based on current information of the condition or the study treatment as outlined in the protocol, investigator's brochure or consent form. Is considered for expedited reporting purposes when the type or event or severity of the event is not listed in the current IB.
- *Expected:* The event is known to be associated with the condition being studied or the intervention.

Expected AES

Expected transient AEs associated with treatment reported occurrence <10%.

- Post nasal drip
- Stinging around mouth
- Pruritus over old BCG scar
- Pruritus over abdomen
- Intermittent abdominal pain
- Mild nausea
- Asthma exacerbation

Serious Adverse Event

Reported occurrence <2%.

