The Principle Investigator provides oversight of the study with assistance from the research coordinator. One of the purported advantages of sublingual administration is greater safety, which allows for administration of this treatment outside of the medical setting.

First dose will occur in medical setting and research coordinator will monitor and record any adverse reactions. Participants will be provided with specific instructions as to how to administer treatment at home and advised to call the research coordinator if bothersome adverse events are experienced. If a dose is missed the participant is not to make up missed dose but resume next scheduled dose. Additionally, the research coordinator will follow-up with each participant within one week of start of treatment to assess any adverse reactions.

The PI will review all study data and any adverse events in real time and reports all SAEs to the study monitor, study safety lead, research ethics board as per local guidelines. AEs are assessed at each study visit by the study team or during review of hospital chart at hospital admission.

All AEs will be assessed and therapeutic strategies implemented according to medical opinion of the PI. Additionally, SAEs will be assessed by the study safety lead.

Occurrence of a UTI

Should a study participant experience a UTI throughout the course of the trial, it will not be captured as an AE. The UTI, along with the symptoms, medical attention and treatment received will be captured through the participant's diary and recorded in the electronic data capture system.

The Investigator must submit sufficient initial information to Health Canada should the SAE report meet the criteria (serious, unexpected and possibly or related to study treatment) for completion of an Adverse Event Drug Reaction Expedited Reporting Summary form and CIOMS report.

As much of the following information about the participant and the event will be requested:

- Participant study code, gender, age, or date of birth
- Underlying diagnosis and extent of disease
- Lot number and expiration date of study drug
- Date of last study drug administration
- Date of death (if applicable)
- Intervention required
- Concomitant medications
- Pertinent laboratory data
- Pertinent medical history
- Study drug status (dose interrupted, discontinued)

- Did event abate after interruption of study drug administration (if applicable)
- Did event recur after study drug was reintroduced (if applicable)

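### The protocol contradicts itself on whether a UTI more severe than expected is an adverse event, and neither rule covers a serious UTI of expected severity

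*Combined protocol and SAP*

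**What the plan says.** Two places in the combined protocol and SAP decide whether a UTI during the trial is an adverse event.

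- *Adverse Event (AE)*, under Safety Reporting, lists what is not an AE. The disease under study is on the list, with recurrent UTI as the example, but with a carve-out: "unless more severe than expected for the" participant's condition.
- *Occurrence of a UTI* has no carve-out: "Should a study participant experience a UTI throughout the course of the trial, it will not be captured as an AE". The episode, its symptoms and its treatment go into the participant diary and then the electronic data capture (EDC) system. No SAE step is mentioned.

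The SAE rules build on AE status. Safety Reporting opens with "The investigator is responsible for the detection and documentation of events meeting the criteria and definition of an AE or SAE". The SAE definition reads "An adverse event is considered serious if any untoward medical occurrence includes any of the following", and criterion (c) is "Event requires in-patient hospitalization or prolongation of existing hospitalization". An SAE must reach the Investigator, study monitor and safety lead within 24 hours of awareness, whether or not it is considered related (the SAE review section). The safety lead assesses SAEs (Risk Mitigation), AEs are reviewed in aggregate each month (Study Monitoring), and the stopping rule counts participants with treatment-emergent SAEs (Interim Analysis Plan and Stopping Rules). Data on the UTI route are due in the EDC within 5 days of a completed visit (Data Management).

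**The concern.** UTI is both the efficacy endpoint and the illness for which every participant is enrolled; one entry route is "at least 3 reported UTI episodes requiring antibiotics in the preceding 12 months". Keeping ordinary episodes out of the AE log is sensible. The difficulty is that the exemption is written twice with different scope, and neither version refers to seriousness. The carve-out in the AE definition turns on severity, whereas SAE status turns on outcomes such as hospitalisation.

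Site staff who follow the more specific section would send even a life-threatening or hospitalised urinary infection to the diary and EDC alone. In an open-label, single-arm study with safety as a joint objective, what is at stake is prompt and independent notice. The Investigator and monitor can see UTI data through real-time review and source verification, but without a 24-hour deadline. The safety lead might hear of the event through discussion with the Investigator or at the monthly review, but no text requires that for a UTI.

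**Working it through.** The plan states no figure on this point, so the main check is a comparison of texts.

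**Step 1. AE status under each rule**

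| UTI during the trial | AE definition | Occurrence of a UTI | Result |
|---|---|---|---|
| More severe than expected, serious | AE, hence SAE | not an AE | conflict |
| More severe than expected, not serious | AE | not an AE | conflict |
| Expected severity, serious | not an AE | not an AE | shared gap |
| Expected severity, not serious | not an AE | not an AE | consistent |

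The conflict acts on the first two rows. The third row is a separate defect: the two rules agree, and both leave the event out.

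**Step 2. How wide the shared gap is**

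The severity scale has Grade 4, "Life threatening or disabling", and Grade 5, death. These overlap seriousness criteria (a) death and (b) life-threatening, and largely (e) disability. A UTI of that kind would readily be judged more severe than expected, so it belongs to the conflict. What remains in the shared gap is mainly criterion (c), hospitalisation. Because the entry condition is UTIs requiring antibiotics, an admission can also be read as more severe than expected, but no text says so.

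**Step 3. Timing**

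SAE: 24 hours from awareness. UTI under the UTI section: EDC entry within 5 days of a completed visit.

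**Step 4. How many participants (assumed rates)**

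The documents give no serious-UTI rate. Let *b* be the assumed 12-month proportion with at least one. Expected number = 80*b*. Chance of at least one = 1 − (1 − *b*)^n, with n = 80 planned, or n = 80 × 0.85 = 68 after the plan's 15% dropout.

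| *b* (assumed) | Expected of 80 | At least one, n = 80 | At least one, n = 68 |
|---|---|---|---|
| 1% | 0.8 | 0.55 | 0.50 |
| 2% | 1.6 | 0.80 | 0.75 |
| 5% | 4.0 | 0.98 | 0.97 |

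These cover all serious UTIs, all of which the UTI section exempts. The AE definition exempts only those of expected severity, a smaller number that the documents do not allow one to split out.

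**Step 5. Stopping count (assumed rates)**

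The rule is more than 20% with treatment-emergent SAEs. At 40 participants that means at least 9 (0.20 × 40 = 8, to be exceeded), although the plan prints 8 in brackets, so both are shown. At 80 it means at least 17. Assume 2% have other SAEs, independent of serious UTIs. If serious UTIs are left out, p = 0.02. If counted, p = 1 − 0.98(1 − *b*), which is 0.0396 at *b* = 2% and 0.069 at *b* = 5%. Binomial tail probabilities:

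| | p | At least 9 of 40 | At least 8 of 40 | At least 17 of 80 |
|---|---|---|---|---|
| Left out | 0.02 | 8.0 × 10⁻⁸ | 1.1 × 10⁻⁶ | 4.0 × 10⁻¹³ |
| Counted, *b* = 2% | 0.0396 | 2.1 × 10⁻⁵ | 1.5 × 10⁻⁴ | 1.3 × 10⁻⁸ |
| Counted, *b* = 5% | 0.069 | 0.0014 | 0.0054 | 2.7 × 10⁻⁵ |

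These are fixed looks. The plan monitors continuously, so they show order of size only.

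**The case against.** The best reply is that a sensible site would report a hospitalised UTI anyway, and much of the text points that way.

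- The UTI section says only that a UTI is not captured as an AE; it does not mention SAEs. The SAE definition speaks of any untoward medical occurrence, and all SAEs must be reported.
- The exemptions under criterion (c) cover routine centre procedures, survey visits or annual physicals, and admissions planned before the study. An unplanned UTI admission is not among them.
- Recording Adverse Events is broad: "All adverse events, which include any detrimental change in the" participant's condition are to be collected.
- The Investigator evaluates each SAE against the participant's underlying condition, so SAEs arising from that condition are foreseen.
- There is hospital chart review, real-time review of all data by the Investigator, review of reporting requirements with the monitor, and 100% source verification.

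This stands to the extent that a miss is less likely than the UTI section alone suggests. It does not remove the defect. None of these provisions overrides an explicit instruction or starts a 24-hour clock for a UTI. Chart review looks for AEs, which the UTI section says a UTI is not. Source verification shows that data match the record, not that the event was classified correctly.

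Some stronger readings are not supported. A reader might infer that the contradiction is what lets a serious UTI of expected severity escape; it is not, since the two rules agree on that case and adopting the AE definition alone would not close the gap. A reader might add the three-month spacing of scheduled contacts to the delay; but the SAE clock runs from awareness, so that spacing affects an SAE equally, and there are also unscheduled visits and a contact within one week of starting treatment. Nor does it follow that expedited reports to Health Canada would be lost: these require an unexpected event, and the Expectedness section classes events associated with the condition as expected, so many serious UTIs might not qualify.

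**Conclusion.** The safety-reporting text is wrong as written, in two respects: a direct conflict over UTIs more severe than expected, and an omission common to both rules for serious UTIs of expected severity. Both follow from the wording and need no assumed rate.

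The consequence is limited. The event still reaches the diary and EDC, and the primary responder analysis is unaffected. What can be lost is the SAE form, the 24-hour notice (chiefly to the safety lead), the safety lead's assessment, a place in the monthly review, and inclusion in the treatment-emergent SAE total. At assumed serious-UTI rates of 1% to 5%, at most about 1 to 4 of 80 participants would be involved.

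It might be inferred that the stopping rule is compromised. At these rates it is not: even in the highest case, counting serious UTIs brings the chance of reaching the limit at 40 participants to only 0.0014, or 0.0054 on the printed count of 8. The point should be fixed for the sake of clear and prompt safety oversight.

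**What to change.** 1. Reconcile the AE definition with Occurrence of a UTI, for example by limiting the exemption in the latter to non-serious UTIs of expected severity.
2. State that a UTI meeting any listed seriousness criterion, (a) to (f), is recorded and reported as an SAE on the 24-hour timeline, whatever its judged severity, and still counts as an efficacy event.
3. State in Interim Analysis Plan and Stopping Rules whether such an event counts toward the treatment-emergent SAE total.

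Item 1 resolves the conflict and item 2 makes the serious case explicit; repeating the severity carve-out in the UTI section would not be enough. The cost is two or three sentences, a CRF completion note, and a few more SAE forms (about 1 to 4 at the assumed rates, if each affected participant has one such event).
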